8.4 Sample Size and Accrual

The target accrual for Cohort 1 was 15 evaluable infants which was projected to require enrolling up to 25 M-I pairs and approximately 12 months to fully accrue. Cohort 1 is fully accrued with 19 evaluable infants (22 M-I pairs).

Cohort 2 will enroll M-I pairs until a total of 15 evaluable infants are accrued which is projected to require enrolling up to 20 M-I pairs. The projected accrual period is 12 months. Evaluable infants will be those who have at least 3 PK blood samples collected following the PK schedule in Section 9.3.

This is a pilot study aimed at gathering information needed for the design of a follow-up study that will evaluate a neonatal raltegravir dosing regimen. The sample size of 15 evaluable infants reflects the judgment of the team pharmacologists with respect to the amount of washout pharmacokinetic data needed to design the later follow-up dosing study. It is based on practical considerations and experience with other antiretroviral drugs such as nevirapine and tenofovir in pregnant women and their neonates [47-50].

All infants enrolled to the study, including those not evaluable for the washout pharmacokinetic analysis, will be included in the safety analyses. The study is not powered for analysis of the safety data so that no hypothesis testing will be done but descriptive summary statistics will be calculated. Given the relatively small study sample, the precision of the estimates will be relatively low and the confidence interval (CI) estimates will be relatively wide. Table 2 shows the precision with which rates of serious adverse events can be estimated, given the sample size of 15, 20 or 25 infants.

Table 2. Point and 90% confidence interval estimates of proportion of infants meeting the toxicity endpoint^a

Number of infants	Proportion of infants meeting toxicity endpoint	90% CI of proportion of infants meeting the toxicity endpoint
15	0.00	(0.00, 0.22)
	0.20	(0.04, 0.48)
	0.40	(0.16, 0.68)
	0.60	(0.32, 0.84)
	0.80	(0.52, 0.96)
	1.00	(0.78, 1.00)
20	0.00	(0.00, 0.17)
	0.20	(0.06, 0.44)
	0.40	(0.19, 0.64)
	0.60	(0.36, 0.81)
	0.80	(0.56, 0.94)
	1.00	(0.83, 1.00)
25	0.00	(0.00, 0.14)
	0.20	(0.07, 0.41)
	0.40	(0.21, 0.61)
	0.60	(0.39, 0.79)
	0.80	(0.59, 0.93)
	1.00	(0.86, 1.00)

^a Clopper-Pearson exact confidence interval estimates using SAS Version 9.2.

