8.6 Analyses

See Section 9.0 for a discussion of PK analyses.

The safety analysis will consist of descriptive statistics summarizing the safety data **through week 20 for Cohort 1 and through week 6 for Cohort 2**. The primary safety analysis will be the calculation of the point and 2-sided 90% confidence interval (CI) using the Clopper-Pearson exact method estimates of the proportion of infants meeting the **composite** toxicity endpoint. Secondary safety analyses will include (1) point and 90% CI estimates of infants meeting each toxicity endpoint; (2) frequency tabulations of worst grade adverse events for each subject; **(3) summary statistics of total and direct bilirubin at each required sampling time and (4) point and 90% CI estimates of infants requiring therapy (e.g. phototherapy, exchange transfusion) to reduce bilirubin.**

A statistical analysis plan specifying details of administrative analyses and full details of primary and secondary analyses of the safety data will be

developed for each cohort. It is expected that analysis of Cohort 2 will combine data from M-I pairs enrolled pre- and post-delivery.

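### The Section 8.4 precision table (Table 2) is labelled 90% Clopper-Pearson, but all 18 printed intervals are two-sided 95% limits

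*Protocol*

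**What the plan says.** Two tables in the protocol carry the number 2. This point concerns the one in Section 8.4, not the unbound-bilirubin table in Section 1.25.

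- **Level.** The Section 8.4 table is headed "Table 2. Point and 90% confidence interval estimates of proportion of infants meeting the toxicity endpoint", and its column header repeats 90%.
- **Method.** The footnote reads "Clopper-Pearson exact confidence interval estimates using SAS Version 9.2".
- **Purpose.** The sentence before the table says: "Table 2 shows the precision with which rates of serious adverse events can be estimated, given the sample size of 15, 20 or 25 infants".
- **Planned analysis.** Protocol 8.6 states: "The primary safety analysis will be the calculation of the point and 2-sided 90% confidence interval (CI) using the Clopper-Pearson exact method". SAP 3.3.1 specifies the same interval for the composite toxicity endpoint.

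Neither document plans a 95% interval for the safety endpoint. The intended level is therefore stated consistently as 90%, two-sided, in the table and in both analysis sections.

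**The concern.** The printed limits look too wide for 90% intervals. The quickest check is the zero-event row for 15 infants, where the exact two-sided 90% upper limit is 0.18 but the table prints 0.22.

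This table is the protocol's only numerical statement of how precisely safety event rates will be estimated. If its limits belong to another confidence level, that precision is misstated. A statistician who checks analysis code against the table would also find a mismatch, and could wrongly conclude that 95% was the intended level.

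**Working it through.** **Inputs.** From the Section 8.4 table: n = 15, 20, 25; proportions p = 0.00, 0.20, 0.40, 0.60, 0.80, 1.00; and the 18 printed intervals. The event count x = n × p is a whole number in every row, so no rounding of counts is needed.

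**Formula.** For a two-sided interval with total error α, the Clopper-Pearson limits are

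- lower = the α/2 quantile of Beta(x, n − x + 1), set to 0 when x = 0;
- upper = the 1 − α/2 quantile of Beta(x + 1, n − x), set to 1 when x = n.

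When x = 0 the upper limit reduces to 1 − (α/2)^(1/n).

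**Zero-event rows.**

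| n | 95%: 1 − 0.025^(1/n) | 90%: 1 − 0.05^(1/n) | Printed |
|---|---|---|---|
| 15 | 0.2180 | 0.1810 | 0.22 |
| 20 | 0.1684 | 0.1391 | 0.17 |
| 25 | 0.1372 | 0.1129 | 0.14 |

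**Rows with p = 0.20 and 0.40.** The rows for 0.60, 0.80 and 1.00 are mirror images of those for 0.40, 0.20 and 0.00.

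| n | x | 95% limits | 90% limits | Printed |
|---|---|---|---|---|
| 15 | 3 | 0.0433, 0.4809 | 0.0568, 0.4398 | 0.04, 0.48 |
| 15 | 6 | 0.1634, 0.6771 | 0.1909, 0.6404 | 0.16, 0.68 |
| 20 | 4 | 0.0573, 0.4366 | 0.0714, 0.4010 | 0.06, 0.44 |
| 20 | 8 | 0.1912, 0.6395 | 0.2171, 0.6064 | 0.19, 0.64 |
| 25 | 5 | 0.0683, 0.4070 | 0.0823, 0.3754 | 0.07, 0.41 |
| 25 | 10 | 0.2113, 0.6133 | 0.2356, 0.5832 | 0.21, 0.61 |

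**Match count.** At α = 0.05, 18 of 18 intervals and 36 of 36 limits agree with the printed values. At α = 0.10, 0 of 18 intervals agree. Only 6 of 36 limits do, and these are the bounds fixed at 0 or 1.

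**Size.** Each of the other 30 limits moves inward by 0.01 to 0.04 at 90%. Dividing the unrounded 95% width by the 90% width gives:

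- p = 0.20 to 0.80: 1.143 (n = 15), 1.150 to 1.151 (n = 20), 1.156 to 1.157 (n = 25);
- p = 0.00 and 1.00: 1.204, 1.211 and 1.215 respectively.

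The printed n = 20 intervals for p = 0.20 to 0.80 are the same, to two decimals, as the true 90% intervals for n = 15. In those rows the table credits 20 infants with the precision that 15 would give at the planned level.

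**Other explanations tried.**

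- Wilson, Agresti-Coull and Wald intervals at 90%, with Wilson and Wald also tried with a continuity correction, reproduce none of the 18 intervals.
- A one-sided 95% limit at zero events is the same as the two-sided 90% limit (0.18 for n = 15), so it does not give the printed 0.22.
- Corrupted text extraction would not yield an exact 95% match in every row.

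A single setting, α = 0.05 in place of 0.10, accounts for the whole table.

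**The case against.** The arithmetic is not open to dispute. The case on the other side is that almost nothing follows from it.

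- Section 8.4 says "The sample size of 15 evaluable infants reflects the judgment of the team pharmacologists", so these intervals did not set the sample size.
- The same section says "The study is not powered for analysis of the safety data so that no hypothesis testing will be done".
- The monitoring committee's criterion in Section 8.5 is accrual, and the protocol team reviews toxicity without a numerical boundary.
- The final analysis will compute its own 90% intervals from observed data, so the table's limits cannot carry into the results.
- The error makes the study look less precise than it is, and the protocol's remark that the intervals will be fairly wide stays true.
- Cohort 1 is closed, and Cohort 2 projects up to 20 pairs. The n = 20 block therefore matters most, and there the zero-event limit changes only from 0.17 to 0.14.
- Because of the mirror-image rows, 18 matches amount to 9 distinct intervals with 15 distinct free limits.

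All of this stands as a limit on the consequence. None of it removes the mismatch: nine distinct matches out of nine still identify the level as 95%, and the table remains wrong for the purpose the protocol gives it.

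**Conclusion.** The concern holds, and it is minor. Every interval in the Section 8.4 table carries a 90% label and a 95% value, so the table understates the precision of the planned 90% safety analysis by the amounts shown above. The conclusion rests only on the printed values, the method named in the footnote and the two-sided reading stated in Protocol 8.6 and SAP 3.3.1; it needs no outside figure or assumption. The analysis method is clearly stated and is not in question. Design, sample size, monitoring and eventual results are unaffected.

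**What to change.** Replace the limits in the Section 8.4 table with the two-sided 90% Clopper-Pearson values:

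| Proportion | n = 15 | n = 20 | n = 25 |
|---|---|---|---|
| 0.00 | (0.00, 0.18) | (0.00, 0.14) | (0.00, 0.11) |
| 0.20 | (0.06, 0.44) | (0.07, 0.40) | (0.08, 0.38) |
| 0.40 | (0.19, 0.64) | (0.22, 0.61) | (0.24, 0.58) |
| 0.60 | (0.36, 0.81) | (0.39, 0.78) | (0.42, 0.76) |
| 0.80 | (0.56, 0.94) | (0.60, 0.93) | (0.62, 0.92) |
| 1.00 | (0.82, 1.00) | (0.86, 1.00) | (0.89, 1.00) |

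Leave Protocol 8.6 and SAP 3.3.1 unchanged. Relabelling the table as 95% would also make it internally correct, but it would then no longer illustrate the planned analysis, so correcting the numbers is the better choice. The cost is one table correction, with no change to enrolment, analysis or monitoring.

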8.5 Monitoring

Reports on accrual and toxicity, compiled by the Data Management Center (DMC), will be reviewed and discussed by the Protocol Team on conference calls held monthly. Conference calls will also be scheduled as needed in response to any adverse event that requires the immediate attention of the Protocol Team. Notification of team members will be by e-mail, phone or fax, depending on time differences.

The safety of maternal transfer of RAL to the neonate will be monitored by means of adverse events reports and toxicity reports presenting laboratory and clinical events. It is the responsibility of the protocol team to interpret the toxicity data, and make any decisions needed to protect subjects from undue risk.

The team will monitor feasibility quarterly, first based on site registration and then on accrual. Initially, the team will monitor site registration quarterly to ensure that an adequate number of sites have registered to complete the protocol. If less than one-third of eligible sites have registered after the protocol has been approved for 6 months, the team will re-assess the feasibility of the protocol and the reasons why sites have not registered, and will amend the protocol accordingly.

See P1097, Version 1.0, for the monitoring of Cohort 1 accrual.

Cohort 2 will be monitored for accrual by a Study Monitoring Committee (SMC) to be appointed per IMPAACT Standard Operating Procedures. The SMC will assess accrual 6 months after Cohort 2 opens to enrollment and protocol version 2.0 has been approved by IRB/ ECs at 50% of eligible sites, and perform an independent review of the data. If Cohort 2 has not met the accrual target subjects (7 eligible infants) by the 6-month timeframe, the protocol team will be required to provide a written plan to increase accrual prior to the SMC 6-month review at which time the SMC will consider whether to recommend closing the study to enrollment.

A full monitoring plan will be developed for each cohort before the cohort opens to accrual. The monitoring plan would include the study monitoring described above as well as the details for monitoring the specimens needed for the pharmacokinetic analyses.

8.6 Analyses

See Section 9.0 for a discussion of PK analyses.

The safety analysis will consist of descriptive statistics summarizing the safety data **through week 20 for Cohort 1 and through week 6 for Cohort 2**. The primary safety analysis will be the calculation of the point and 2-sided 90% confidence interval (CI) using the Clopper-Pearson exact method estimates of the proportion of infants meeting the **composite** toxicity endpoint. Secondary safety analyses will include (1) point and 90% CI estimates of infants meeting each toxicity endpoint; (2) frequency tabulations of worst grade adverse events for each subject; **(3) summary statistics of total and direct bilirubin at each required sampling time and (4) point and 90% CI estimates of infants requiring therapy (e.g. phototherapy, exchange transfusion) to reduce bilirubin.**

A statistical analysis plan specifying details of administrative analyses and full details of primary and secondary analyses of the safety data will be

developed for each cohort. It is expected that analysis of Cohort 2 will combine data from M-I pairs enrolled pre- and post-delivery.

9.0 CLINICAL PHARMACOLOGY PLAN

9.1 Pharmacology Objective

The clinical pharmacology objective of this study is to estimate raltegravir elimination ($t_{1/2}$) in neonates born to women receiving raltegravir as part of HAART during pregnancy. When P1066 pharmacokinetic data are available for the 4 weeks to <2 year old cohort, there will be a much better understanding of infant dosing, and bioavailability of the new oral granules for suspension formulation will be known. Those data, coupled with data collected from this study examining the raltegravir washout pharmacokinetics in neonates born to women receiving raltegravir, will provide a more solid foundation upon which to base the design of the later follow-up study (active single dose and multiple dose raltegravir pharmacokinetic studies in infants).

9.2 Primary and Secondary Data

Demographic data and recent dosing history including food intake, delivery information and sample collection times will be collected. The goal is to estimate clearance in the infants and provide guidance on when to initiate dosing, dose and dosing regimen in the infants for the later (active single dose and multiple dose) follow-up study.

Information obtained about the effect of UGT1A1 polymorphisms on the pharmacokinetics of raltegravir will provide a better understanding of the effect of genetics on the metabolism of raltegravir in neonates.

Laboratory Analysis and Reporting

Blood samples will be collected in standard EDTA tubes. Frozen plasma will be batched and shipped to the University of Alabama Pharmacology Specialty Laboratory (UAB PSL). All PK samples and results will be registered in the Laboratory Data Management System (LDMS) database.

Raltegravir concentrations will be measured using a validated HPLC-MS-MS method [51].

9.3 Study Design, Modeling and Data Analysis

Cohort 1 (Closed)

There will be no infant dosing for this study. Women must have received at least two weeks of raltegravir prior to delivery and continue to receive raltegravir during labor prior to delivery as well as their other ARVs.

Maternal raltegravir concentration: One maternal blood sample will be obtained within one hour after delivery. In addition, a single cord blood specimen will be collected at the time of birth.

Neonatal: Blood samples for raltegravir concentration determinations will be collected between 1-5, 8-14, 18-24, and 30-36 hours post-delivery. Sample times chosen will allow for flexibility at the sites for the collection of raltegravir concentrations. The first pharmacokinetic sample will be close to the time of the peak raltegravir concentration while the next three samples will be collected during the elimination phase.

Cohort 2

There will be no infant dosing for this study. Women must have received at least one dose of raltegravir within 2 to 24 hours prior to delivery. Dose must be administered at least 2 hours prior to delivery to allow adequate time for absorption and distribution.

Maternal and cord blood raltegravir concentrations: When possible, for example, pre-delivery enrollment, one maternal blood sample will be obtained within one hour after delivery and a single cord blood specimen at the time of birth. For infants enrolled after delivery up to 48 hours after birth, it will not be possible to obtain maternal or cord blood samples.

Neonatal raltegravir concentrations: Blood samples for raltegravir assay will be collected at 1-6, 12-24, 36-48, 72-84, and 108-132 hours after birth, and on day 7-14. Infants may enroll up to 48 hours of age, and any pharmacokinetic samples scheduled for collection prior to the time of enrollment will be skipped and not replaced. Infants enrolling close to the 48-hour time point should have the first pharmacokinetic blood sample collected within 4 hours of enrollment (i.e., within 52 hours after birth) so that a minimum three blood samples can be obtained for pharmacokinetic evaluation.

Analysis for Cohort 1 and Cohort 2

Regression analysis will then be used to estimate the terminal phase of raltegravir elimination in the neonates. Since this study will not include a full intensive PK evaluation we will not have an estimate of distribution volume and thus clearance cannot be calculated directly. To resolve this, we will assume the same average distribution volume from subjects ≥ 4

weeks to <6 months of age in Cohort V in P1066 to calculate raltegravir clearance in the neonates. This will provide an initial estimate of the dose required in neonates to produce a similar AUC compared to the youngest P1066 cohort.

9.4 Anticipated Outcomes

The goal is to estimate raltegravir clearance in **both term and low birth weight** neonates following maternal dosing of raltegravir as part of HAART. These data, along with those collected from P1066 will assist in understanding how to dose this drug in the neonatal population.

10.0 HUMAN SUBJECTS

10.1 Institutional Review Board and Informed Consent

This protocol, the informed consent documents (Appendix IV-A and IV-B), and any subsequent modifications must be reviewed and approved by the Institutional Review Board (IRB) or Ethics Committee (EC) responsible for oversight of the study. Written informed consent must be obtained from the parents or legal guardians of subjects who cannot consent for themselves, such as those below the legal age. The informed consent will describe the purpose of the study, the procedures to be followed, and the risks and benefits of participation. A copy of the consent form will be given to the parent or legal guardian.

Each site which receives US HHS funding and follows the United States Code of Federal Regulations Title 45-Public Welfare, Part 46-Protection of Human Subjects (also known as the Common Rule) should have on record at the site a plan that detects and addresses any change in guardianship occurring in pediatric subjects and determines when a study subject must have a consent process which involves a legally authorized representative (LAR) other than a family member with guardianship. The plan will include how the site determines when a LAR is initially or no longer needed and how frequently the LAR re-signs the consent. The plan should follow all IRB/EC, local, state, national and/or host country guidelines. Confirmation of such a plan at a site should be submitted with protocol registration materials.

10.2 Subject Confidentiality

All laboratory specimens, evaluation forms, reports, and other records will be identified only by a coded number to maintain subject confidentiality. All records will be kept in a secured area. All computer entry and

networking programs will be done with coded numbers only. Clinical information will not be released without written permission of the subject, except as necessary for monitoring by the study staff, study monitors, drug company supporting the study, and designees, the OHRP, NIH, FDA, or the local IRB/EC.

10.3 Study Discontinuation

The study may be discontinued at any time by the IMPAACT network, the OHRP, NIH, FDA, or local IRB/EC, the pharmaceutical sponsor, or other governmental agencies as part of their duties to ensure that research subjects are protected.

11.0 PUBLICATION OF RESEARCH FINDINGS

Publication of the results of this trial will be governed by IMPAACT policies. Any presentation, abstract, or manuscript will be made available for review by the pharmaceutical sponsors prior to submission.

12.0 BIOHAZARD CONTAINMENT

As the transmission of HIV and other blood borne pathogens can occur through contact with contaminated needles, blood, and blood products, appropriate blood and secretion precautions will be employed by all personnel in the drawing of blood and shipping and handling of all specimens for this study, as currently recommended by the Centers for Disease Control and Prevention.

All infectious specimens will be sent using the ISS-1 SAF-T-PAK mandated by the International Air Transport Association Dangerous Goods Regulations-Packing Instruction 602. Refer to individual carrier guidelines (e.g., Federal Express or Airborne) for specific instructions.

APPENDIX I-A

COHORT 1 MATERNAL SCHEDULE OF EVALUATIONS (CLOSED)

	Screening	Labor/delivery
Informed Consent	X	
CLINICAL EVALUATIONS		
History	X ¹	X ²
PHARMACOKINETICS		
Maternal RAL concentration ³		1mL
OTHER		
Cord Blood ⁴		1mL
TOTAL BLOOD		2mL

1. Obtain complete history including documentation of HIV-1 infection, demographic data and antiretroviral medications.
2. Obtain complete history including maternal antiretroviral dosing history, labor and delivery record, and obstetrical gestational age.
3. Collect 1mL of blood within one hour after delivery.
4. Draw 1mL of cord blood immediately after cord is clamped.

APPENDIX I-B

COHORT 2 MATERNAL SCHEDULE OF EVALUATIONS

	Screening/entry	Labor/delivery ⁶	Post-Delivery (1-5 days after delivery)
Informed Consent	X		
CLINICAL EVALUATIONS			
History	X ¹	X ²	X ²
PHARMACOKINETICS⁷			
Maternal RAL concentration ³	1mL ⁴ If enrolled after delivery	1mL ⁴ If enrolled before delivery	
OTHER ⁷			
Cord Blood ^{3,5}		X	
TOTAL BLOOD	1mL	1mL	0mL

1. History data at Screening/entry includes documentation of HIV-1 infection, demographic data and antiretroviral dosing history 3 months prior to entry.
2. History data after Screening/entry includes antiretroviral dosing while on study, labor and delivery record, and obstetrical gestational age. It is strongly recommended that the site report, prospectively if possible, the mother to the Antiretroviral Pregnancy Registry (<http://www.apregistry.com/reg.htm>):
 US/Canada [contact], [contact]
 Brazil: [contact]
 International: [contact], [contact]
 Email: [contact]
3. Mother/infant pairs may be enrolled up to 48 hours after delivery. In these situations it may not be possible to collect the maternal and cord blood samples at labor and delivery.
4. For women enrolled prior to delivery, collect 1mL of maternal blood within one hour after delivery. For women enrolled after delivery, collect 1mL of maternal blood at the time of enrollment.
5. Draw cord blood immediately after cord is clamped.
6. Not applicable to women enrolled after delivery.
7. See the Laboratory Processing Chart (LPC) on the P1097 Protocol Specific Webpage on the IMPAACT website (<http://www.impaactgroup.org>) for collection, processing and shipping instructions.

